3.2 Study Flow Chart

Visit Number	Visit 1	Visit 2	Visit 3	Visit 4	Visit 5	Visit 6 ^a	Retreated Subjects Only			
							Visit 7	Phone contact	Visit 8	
Scheduled Day (Week)	Day 1 (Week 0)	Day 7 (Week 1)	Day 14 (Week 2)	Day 28 (Week 4)	Day 84 (Week 12)	Day 168 (Week 24)	Day 196 (Week 28)	Day 280 (Week 40)	Day 364 (Week 52)	Unsched Visit
Scheduling Window	none	± 2 days	± 2 days	± 4 days	± 4 days	± 7 days	± 7 days	± 7 days	± 7 days	
Informed consent	X									
Medical history/ demographics	X									
Physical examination (including vital signs)	X									
Concomitant Medication/ Treatment	X	X	X	X	X	X	X	X	X	X
Inclusion/exclusion criteria review	X									
Urine pregnancy test ^c	X									
Wrinkle Severity Rating Scale (WSRS)	X	X	X	X	X	X	X		X	X ^b
Randomization	X									
Treatment with study products	X					X ^a				
Investigator Ease of Use	X									
Patient Comfort Rating (PCR)	X	X ^d								
Evaluation for touch-up		X								
Patient GAI (pGAI)		X	X	X	X	X	X		X	X ^b
Investigator GAI (iGAI)		X	X	X	X	X	X		X	X ^b
Adverse event assessment	X	X	X	X	X	X	X	X	X	X
Subject Diary	Dispense	Review/ Dispense ^b	Collect	Collect ^b		Dispense ^b	Collect ^b			
Schedule/confirm next visit	X	X	X	X	X	X ^a	X	X		X ^b

a Subjects may be retreated with open-label Revanesse Ultra if scores have returned to baseline or to achieve optimal correction if the baseline scores have not returned to baseline; for subjects who are not retreated, Visit 6 is End of Study.

b If applicable.

c For women of childbearing potential, to be completed prior to enrollment.

d For subjects who receive a touch-up treatment

Confidential

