8.3.2 Exclusion Criteria

Subjects who meet any of the following criteria will be excluded from the study:

1. Wrinkle Severity Rating Scale Score of ≤ 2 on the right or left nasolabial fold.
2. Women who are pregnant or lactating.
3. Received prior dermabrasion, facelift, or Botox below the orbital rim within 6 months (180 days) prior to entry into the study.

4. Previous tissue augmentation (bulking agents) for facial wrinkles and scars within 6 months (180 days) at the proposed injection sites.
5. Previous tissue augmentation with permanent implants.
6. Evidence of scar-related disease or delayed healing activity within the past 1 year.
7. Scars at the intended treatment sites.
8. History of keloid formation or hypertrophic scars.
9. Any infection or wound on the face.
10. Allergic history including anaphylaxis or multiple severe allergies to natural rubber latex or lidocaine.
11. Aspirin or nonsteroidal anti-inflammatory drugs within 1 week (7 days) prior to treatment.
12. Concomitant anticoagulant therapy, antiplatelet therapy, or history of bleeding disorders or connective tissue disorders.
13. Over-the-counter (OTC) wrinkle products or prescription wrinkle treatments within 4 weeks (28 days) prior to treatment and throughout the study.
14. Immunocompromised or immunosuppressed.
15. Clinically significant organic disease including clinically significant cardiovascular, hepatic, pulmonary, neurologic, or renal disease or other medical condition, serious intercurrent illness, or extenuating circumstance that, in the opinion of the investigator, preclude participation in the trial.
16. Received any investigational product within 30 days of signing the Informed Consent Form.
17. Facial tattoo that may interfere with diagnosis.
18. Systemic (oral/injectable) corticosteroids or immunosuppressive medications within 30 days prior to treatment and topical steroids on the face within 14 days prior to treatment start and throughout the study.

8.3.3 *Subject Withdrawal Criteria*

A subject may withdraw from the study at any time for any reason.

A subject will be withdrawn from the study if his/her safety or well-being is determined to be at risk. Withdrawal will be made at the discretion of the investigator or at the subject's request.

A subject must withdraw from the study for any of the following reasons:

- The subject or legal representative withdraws consent
- The subject's product code is unblinded
- There is a significant protocol violation

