The subject should be injected so that an optimal correction is achieved. If overcorrected, massage firmly between fingers or against underlying bone to obtain optimal results. Approximately 20% overcorrection can be massaged out; more will lead to a persistent unwanted cosmetic result.

Optional Retreatment at 6 Months

At Visit 6/Week 24, the subject may be retreated with Revanesse Ultra, and treatment will be open-label. Subjects will be eligible for retreatment when WSRS scores have returned to baseline for either or both NLFs. If scores have not returned to baseline, subjects are also eligible to be injected for either one or both NLFs as needed to achieve optimal correction. The retreatment group and the optimal correction group will be separated for data analysis.

8.4.4 *Blinding of Study Product*

Injections of the study product prior to Week 24 are performed by the unblinded injecting investigator. The blinded evaluator is not allowed to retrieve study supplies or to be present during opening of the study supplies or during the injections. The injecting investigator is not to have any discussion with the blinded evaluator or subjects regarding the treatments.

Subjects are blinded to treatment assignment of each NLF. Subjects are physically masked (blindfolded) just prior to and during all injection procedures to prevent observation of the syringes containing study product.

Subjects, investigators, the sponsor's staff conducting the study, and members of the administrative team will not have access to individual subjects' treatment assignments. In the event of an emergency that requires breaking of the study blind, randomization code envelopes will be maintained by each investigator that can be opened to reveal the study product.

See [Section 8.9.6.2](#) for a description of the method of unblinding a subject during the study if such action is warranted.

Retreatment with Revanesse Ultra at Week 24 is unblinded. Subjects being retreated do not need to be masked and retreatment may be administered by a qualified investigator or evaluator.

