8.6.6 Urine Pregnancy Test and Acceptable Contraceptive Methods

Women of childbearing potential, in addition to having a negative urine pregnancy test at Visit 1/Day 1, must be willing to use an acceptable form of birth control during the study. The following are considered acceptable methods of birth control for the purpose of this study: oral contraceptives, contraceptive patches, contraceptive implant, vaginal contraceptive, double barrier methods (e.g., condom and spermicide), contraceptive injection (Depo-Provera®), IUD, hormonal IUD (Mirena®), and abstinence with a documented second acceptable method of birth control if the subject becomes sexually active. Subjects entering the study who are on hormonal contraceptives must have been on the method for at least 90 days prior to the study and continue the method for the duration of the study. Subjects who had used hormonal contraception and stopped must have stopped no less than 90 days prior to Visit 1/Day 1.

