8.7.1 Visit 1/Day 1: Baseline and Treatment

1. Obtain written informed consent ([Section 8.6.2](#))
2. Obtain medical history and demographic information, including Fitzpatrick skin type classification ([Section 8.6.3](#))
3. Perform physical examination, including height, weight, and vital signs (temperature, heart rate, blood pressure, and respiratory rate) ([Section 0](#))
4. Obtain/record prior and concomitant medications/treatments ([Section 8.6.5](#))
5. Perform urine pregnancy test for all women of childbearing potential ([Section 8.6.6](#))
6. WSRS assessment ([Section 8.6.7](#))
7. Evaluate inclusion/exclusion criteria ([Section 8.3](#))
8. Randomization ([Section 8.4.2](#))
9. Treatment administration ([Section 8.4.3](#))
10. Investigator Ease of Use assessment ([Section 8.6.9](#))
11. PCR assessment ([Section 8.6.10](#))

12. Assess AEs ([Section 8.9](#))
13. Dispense subject diary card ([Section 8.6.14](#))
14. Schedule next visit
15. Complete CRFs ([Section 11.2.1](#))

8.7.2 *Visit 2/Day 7 (± 2 days), Visit 3/Day 14 (± 2 days), Visit 4/Day 28 (± 4 days), and Visit 5/Day 84 (± 4 days): Interim Visits*

1. WSRS assessment ([Section 8.6.7](#))
2. At Visit 2/Day 7 only, evaluation for touch-up ([Section 8.6.11](#))
3. PCR assessment if a touch-up treatment is administered ([Section 8.6.10](#))
4. pGAI assessment ([Section 8.6.12](#))
5. iGAI assessment ([Section 8.6.13](#))
6. Assess AEs ([Section 8.9](#))
7. Assess concomitant medications ([Section 8.6.16](#))
8. Collect subject diary card at Visit 3/Day 14; dispense subject diary card at Visit 2/Day 7, if applicable and collect subject diary card at Visit 4/ Week 4 if applicable ([Section 8.6.14](#))
9. Schedule next visit
10. Complete CRFs ([Section 11.2.1](#))

8.7.3 *Visit 6/Day 168 (Week 24) (± 7 days): Optional Retreatment or Final Visit/Early Termination*

1. WSRS assessment ([Section 8.6.7](#))
2. pGAI assessment ([Section 8.6.12](#))
3. iGAI assessment ([Section 8.6.13](#))
4. Assess AEs ([Section 8.9](#))
5. Assess concomitant medications ([Section 8.6.16](#))
6. Subjects may be retreated with Revanesse Ultra open-label on both sides of the face if their WSRS scores have returned to baseline or to achieve optimal correction ([Section 8.4.3](#))
7. Dispense subject diary card if subject was retreated ([Section 8.6.14](#))
8. Schedule next visit for retreated subjects
9. Complete CRFs ([Section 11.2.1](#))

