8.9.2.6 Pregnancy

Pregnancies occurring after the administration of study product require immediate reporting. They must be reported within 24 hours after the investigator has become aware of the pregnancy. A pregnancy report will be completed and sent by fax to Symbio within 24 hours of becoming aware of the pregnancy. The investigator will collect follow-up information regarding the outcome of the pregnancy and any postnatal sequelae in the infant that must also be reported to the sponsor or designee. Upon awareness of the outcome of the pregnancy, the PI or designee must forward a follow-up Pregnancy Report with any relevant information to Symbio.

If the outcome of the pregnancy meets the criteria for immediate classification of an SAE (e.g., spontaneous abortion, stillbirth, neonatal death, or congenital anomaly), the investigator will report the event by faxing a completed SAE report form to Symbio within 24 hours of being notified of the pregnancy report.

The subject should immediately be withdrawn from the study.

8.9.2.7 *Monitoring*

8.9.3 *Monitoring Adverse Events and Laboratory Evaluations*

Each subject will be monitored for the occurrence of AEs, including SAEs, immediately after treatment initiation. Each subject will be followed for safety monitoring until discharged from the study. Follow-up procedures related to pregnancy or AEs or SAEs may continue beyond the end of the study.

Subjects will be questioned and/or examined by the investigator or a qualified designee for occurrence of AEs throughout the study. The presence or absence of specific AEs should not be elicited from subjects. In addition, subjects will be instructed to record AEs on the subject diary card during the 2 weeks after treatment. Subjects having AEs will be monitored with relevant clinical assessments and laboratory tests, as determined by the investigator.

AEs, actions taken as a result of AEs, and follow-up results must be recorded on the CRF, as well as in the subject's source documentation.

For all AEs that require the subject to be withdrawn from the study and SAEs, relevant clinical assessments and laboratory tests will be repeated as clinically appropriate until final resolution or stabilization of the event(s).

8.9.4 *Assessment of Adverse Events*

8.9.4.1 *Assessment of Severity*

Severity of AEs will be graded according to the following definitions:

Mild: AE that was easily tolerated

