15 APPENDICES

15.1 Package Insert for Revanesse Ultra

COMPOSITION

Cross-linked hyaluronic acid (High Viscosity) 25mg/ml
In phosphate buffered saline
[Cross linked with Butandiol-diglycidylether (BDDE)]

DESCRIPTION

Revanesse® Ultra is a colorless, odorless, transparent and aqueous gel of synthetic origin. The gel is stored in a pre-filled disposable syringe. Each box contains two 1ml syringes of Revanesse® Ultra along with two sterilized needles.

APPLICATION RANGE / INDICATIONS

Revanesse® Ultra is a cross linked hyaluronic acid gel that is indicated for the filling of medium size and deep wrinkles of the face by injection into the middle part of the dermis layer. Implantation life is dependent on depth and location and averages 6-12 months.

ANTICIPATED SIDE EFFECTS

Physicians must inform patients that with every injection of Revanesse® Ultra there are potential adverse reactions that may be delayed or occur immediately after the injection. These include but are not limited to:

- Injection-related reactions might occur, such as transient erythema, swelling, pain, itching, discoloration or tenderness at the injection site. These reactions may last for one week.
- Nodules or induration are also possible at the injection site.
- Poor product performance due to improper injection technique.
- Glabellar necrosis, abscess formation, granulomas and hypersensitivity have all been reported with injections of hyaluronic acid products. It is important for physicians to take these reactions into account on a case by case basis.

Reactions thought to be of hypersensitivity in nature have been reported in less than one in every 1500 treatments. These have consisted of prolonged erythema, swelling and induration at the implant site.

These reactions have started either shortly after injection or after a delay of 2 - 4 weeks and have been described as mild or moderate, with an average duration of 2 weeks. Typically, this reaction is self-limiting and resolves spontaneously with time. However, it is imperative that patients with hypersensitivity type reactions contact their physician immediately for assessment. Patients with multiple allergic reactions should be excluded from the treatment.

CONTRAINDICATIONS

- Do not inject Revanesse® Ultra into eye contours (into the eye circle or eyelids).
- Pregnant women, or women during lactation should not be treated with Revanesse® Ultra.

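### The only pregnancy test is at Visit 1, so the elective Week 24 reinjection can be given on a test nominally 160 to 174 days old

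*Protocol*

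**What the plan says.** **The test.** The flow chart (3.2) has one mark for the urine pregnancy test, under Visit 1, with footnote c: "For women of childbearing potential, to be completed prior to enrollment". Section 8.6.6 says the same, requiring contraception "in addition to having a negative urine pregnancy test at Visit 1/Day 1", and section 8.7.1 lists the test as step 5 of Visit 1. No later visit list includes it.

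**The second injection.** The same flow chart marks treatment with study product at Visit 1 and at Visit 6. Section 8.7.3 makes it step 6 of Visit 6: "Subjects may be retreated with Revanesse Ultra open-label on both sides of the face if their WSRS scores have returned to baseline", or to reach optimal correction. Section 8.4.3 gives the eligibility rule in two parts: "Subjects will be eligible for retreatment when WSRS scores have returned to baseline for either or both NLFs", and "If scores have not returned to baseline, subjects are also eligible to be injected for either one or both NLFs" as needed. Both parts turn on the wrinkle score (WSRS) or on cosmetic judgement.

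**Pregnancy elsewhere in the protocol.** Exclusion 2 in section 8.3.2 reads "Women who are pregnant or lactating". The Revanesse Ultra insert in appendix 15.1 lists as a contraindication: "Pregnant women, or women during lactation should not be treated with Revanesse® Ultra". Section 8.9.2.6 adds: "Pregnancies occurring after the administration of study product require immediate reporting", within 24 hours of the investigator becoming aware, with follow-up to outcome and withdrawal of the subject.

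**The concern.** The protocol requires a negative test before the first injection of a product that it treats as contraindicated in pregnancy. It then allows a second, elective injection of that product about half a year later without repeating the test, and gives no reason for handling the two injections differently. Entry is open from age 22 with no upper limit, and women of childbearing potential are expressly admitted (8.3.1). A site that follows the text exactly could inject a woman who is pregnant and does not know it. The stake is subject safety. The treatment is cosmetic and can be deferred at little cost, so there is little to set against that risk.

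**Working it through.** No sample size, power or error-rate figure enters this point. The check has three parts.

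**1. Age of the last test at the second injection.**
- Inputs: the test is done on Day 1 (8.6.6, 8.7.1); visits are timed relative to Day 1 (8.5); Visit 6 is Day 168 ± 7 days (3.2, 8.7.3).
- Visit 6 window: 168 − 7 = Day 161 to 168 + 7 = Day 175.
- Days since the test: 161 − 1 = 160 to 175 − 1 = 174.
- In weeks: 160 / 7 = 22.9 to 174 / 7 = 24.9.
- Reading Day 168 as 168 elapsed days would give 161 to 175 days. The one-day difference does not matter.
- These are nominal figures. Section 8.5 lets a missed visit be scheduled as near the window as possible, so the real gap can fall outside the range.

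**2. Gap before Visit 6.**
- Visit 5 is Day 84 ± 4 days, so Day 80 to Day 88.
- Shortest gap to Visit 6: 161 − 88 = 73 days. Longest: 175 − 80 = 95 days.
- The flow chart schedules no contact in that interval.

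**3. Whether another step would catch an unrecognised pregnancy.**
- *Contraception during the study* (8.3.1, 8.6.6) makes pregnancy less likely. It detects nothing.
- *Medication review* (8.6.16; step 5 of Visit 6, before retreatment) could show that a prescribed hormonal contraceptive was stopped. It does not cover non-drug methods and does not show pregnancy.
- *Adverse event assessment* (8.9.3; step 4 of Visit 6) could bring out a pregnancy that the subject knows of. The questioning is deliberately non-leading, so no one is told to ask about pregnancy.
- *Reporting and withdrawal* (8.9.2.6) starts only when the investigator is aware.
- *Withdrawal of a subject at risk* (8.3.3) also needs prior knowledge.
- *Restriction of product to subjects who met entry criteria* (8.4.5) refers to criteria that the flow chart reviews at Visit 1 only.

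Each step either lowers the chance of pregnancy or acts on one already known. With a repeat test at Visit 6, the gap in part 1 falls from 160 to 174 days to 0 days.

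**The case against.** **The protocol is consistent.** The flow chart and sections 8.6.6, 8.7.1 and 8.7.3 all specify one entry test followed by contraception. That is right. This is a design choice that can be improved, and a reader should not take it for a contradiction.

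**The safeguards are substantial.** Contraception must be used throughout, and hormonal users must have been on their method for at least 90 days and must continue it. A known pregnancy leads to withdrawal. A reader might infer that the protocol would let a woman known to be pregnant be retreated; section 8.9.2.6 rules that out. What remains is the unrecognised pregnancy despite required contraception.

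**The size is unknown and the harm unspecified.** The protocol gives neither the share of women of childbearing potential nor the expected uptake of retreatment. The only age context comes from a different trial: a nasolabial-fold study of 75 subjects in the appended Restylane insert, with mean age 53.8 and median 54, which suggests a minority. Neither insert describes a specific fetal harm, and the Revanesse Ultra insert does not ask for testing. All of this stands, and it limits the weight of the point. It does not remove it, because the protocol itself thought a test necessary before the first injection.

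**A wider re-check.** A reader might infer that every entry criterion should be reviewed again before retreatment. The documents do not support this. Exclusion 4 bars augmentation at the proposed injection sites within 180 days, and a Visit 6 in window falls 160 to 174 days after both folds were filled, so every such subject would be barred. Exclusion 1 bars a score of 2 or less on either fold, which would shut out improved subjects whom section 8.4.3 deliberately admits for optimal correction.

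**Conclusion.** The point holds as a cheap improvement for patient safety. Followed exactly, the protocol permits an elective injection that its own appended insert contraindicates, in a woman whose last negative test is nominally 160 to 174 days old, with no step that would reveal an unrecognised pregnancy.

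The conclusion assumes that visits occur within their windows and that the visit lists in section 8.7 are complete, as that section says. The number of women affected cannot be estimated and is probably small.

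A reader might infer that the Week 24 efficacy result is at risk. It is not: the WSRS is step 1 of Visit 6 and retreatment is step 6, so the primary endpoint is recorded before any second injection.

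**What to change.** Four edits:

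1. **Flow chart 3.2:** mark the urine pregnancy test at Visit 6 as well, and extend footnote c to cover women of childbearing potential who are to be retreated, tested before the injection.
2. **Section 8.7.3:** insert the test after the WSRS, pGAI and iGAI assessments and before step 6. Because section 8.9.2.6 calls for immediate withdrawal, this order keeps the Week 24 efficacy data of a woman who tests positive.
3. **Section 8.4.3:** make a negative Visit 6 result a condition of retreatment for these women, with a positive result handled under the existing section 8.9.2.6.
4. **Section 8.6.6:** name Visit 6 alongside Visit 1.

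The cost is one urine test, of a kind the trial already uses, per retreated woman of childbearing potential, at a visit that already takes place. The downside is an occasional retreatment withheld. No sample size or analysis changes.

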8.8 Efficacy Assessments

8.8.1 Primary Efficacy Endpoint

The primary efficacy endpoint is change from baseline to Visit 6/Week 24 in WSRS score. The WSRS is a validated scale (Day et al, 2004).

8.8.2 Secondary Efficacy Endpoints

Secondary efficacy endpoints are the responder rate, i.e., the percentage of subjects with treatment success (defined as at least a 1-grade improvement in WSRS from baseline to Week 24), pGAI score at Visit 6/Week 24, and iGAI score at Visit 6/Week 24.

8.8.3 Other Efficacy Endpoints

Other efficacy endpoints include change in WSRS score, pGAI, and iGAI at Visit 2/Week 1, Visit 3/Week 2, Visit 4/Week 4, and Visit 5/Week 12.

8.9 Assessment of Safety

8.9.1 Safety Endpoints

Safety of the study products will be compared by evaluating the nature, severity, and frequency of treatment-emergent adverse events (TEAEs). All AEs that occur during the study will be recorded whether or not they are considered to be related to treatment. A description of the AE will be recorded with the date of onset, date of resolution, severity of the AE, relationship to the study product, action taken, and the outcome.

8.9.2 Definitions of Terms

8.9.2.1 Adverse Event

An AE is defined as any untoward medical occurrence associated with the use of a drug in humans, whether or not considered drug-related (21 Code of Federal Regulations [CFR] 312.32 (a)). An AE can therefore be any unfavorable and unintended sign (including an abnormal laboratory finding, for example), symptom, or disease temporally associated with the use of a drug, without any judgment about causality.

Expected adverse events are defined as the events that appeared at injection site subsequent to the first injection. Expected adverse events may include but are not limited to bruising, swelling, erythema, edema, inflammation at injection site.

